### **Eligibility.**

For incarcerated individuals, inclusion criteria:

- English speaking
- Over the age of 18
- Diagnosed with opioid use disorder

Exclusion Criteria:

- Diagnosed with "Severe, Persistent, Mental Illness (SPMI)"

Rationale for Exclusion: *These individuals suffer from severe mental health disease and therefore warrant greater protection, have greater risk for coercion, and offer insights to severe co-diagnosis treatment that, while important, remain outside the scope of general MAT implementation.*

### **FOR ORGANIZATIONAL STAKEHOLDERS:**

Inclusion Criteria:

- Employed or contracted by Rhode Island Department of Corrections (for organizational staff interviews) and involved with the Medication for Addiction Treatment (MAT) program

Exclusion Criteria:

- If not permitted by their organizational union to participate

**Data Storage.** All participant data will be kept confidential. Survey data will be anonymous. Qualitative interview data will be kept confidential. Audio will be collected on password-protected digital voice recorders. Audio files and transcripts will be identified by participant ID only. The participant's identification number will only be connected to the participant's name through a single encrypted password-protected master file kept on password-protected computers, accessible only to approved research staff. We will protect all other data files with passwords and lock any paperwork in cabinets. Transcripts will be the primary data source after audio is deleted. Audio files will be deleted on a monthly review basis after transcripts have been certified per methodology below. Survey data will be password protected in a secure REDCAP server and paper copies will be kept in a locked cabinet in a locked office with research staff access only. Surveys will be anonymous.

The study will also be approved by the Medical Research Advisory Group (MRAG) at the Rhode Island Department of Corrections (RIDOC). All research will be conducted in a manner consistent with the highest ethical standards using these multiple oversight groups as well as collaboration with the COBRE for Opioids and Overdose Community Advisory Board and in line with previous NIH-supported research conducted at the RIDOC.

### **METHOD AND PROCEDURES:**

**In-depth Interviews (IDI).** Interviews (60-90 min) will be scheduled with stakeholders and guided by well-established qualitative methodology practices in implementation research. Interviews will be audio-recorded and transcribed verbatim. A debriefing template29(p30) will be used after every interview to assess process issues, evaluate data quality, and consider

saturation. Interviews will continue until data analysis reflects saturation. All participants will receive \$25 reimbursement for their time via electronic gift-card or commissary deposit, as has been done in previous studies approved by the IRB and the RIDOC.

**Surveys.** The NIH JCOIN has developed standardized measures implemented across multiple correctional facilities to harmonize data. Measures used in this study will include: Organizational Readiness for Implementing Change (ORIC), Staff Attitudes Toward MOUD (SATM), and Implementation Outcome Measures. These are NIH-endorsed survey measures. Each survey is very short (under 15 Likert-style questions each). Enrollment of 20 stakeholders or more should be very feasible based on similar studies with similar participation at the RIDOC. All survey data will be anonymous and on paper. A member of the research team will input data into a secure server using REDCap, original paper documents will be locked in the office of the PI.

**Risks.** This study will have minimal risk, described below.

**Study Site:** Rhode Island Department of Corrections.

**Study Start Date.** Within 1 month of IRB and MRAG approval.

**Study End Date:** Upon saturation (anticipated within 3 – 6 months).

**Interview Guide.** An open-ended interview guide has been developed based on existing literature and with input from the COBRE Community Engagement Research Core. *The core qualitative research question* will be: What are the barriers and facilitators to successful uptake of XR-B? As common practice in implementation research, the interviews will be shaped by a conceptual framework, in this case, iPARIHS. A preliminary interview guide is attached though will be revised in an iterative process based on emerging themes. As described in the guide, questions will not be verbatim but ensure all content areas are discussed. Interviews with patients will have greater emphasis on Recipient and Innovation domains, while interviews with other stakeholders will focus on Context and Facilitation domains.

**Surveys.** Copies of (1) Organizational Readiness for Implementing Change (ORIC), (2) Staff Attitudes Toward MOUD (SATM), and (3) Implementation Outcome Measures are attached. Paper forms will be completed by organizational stakeholders (without name or other PHI) and will be entered into REDCap secure software to record results. Original copies of survey sheets will be locked in the PI's office.

**This research will not affect standard treatment or routine care in any way.**

**Data Collection and Analysis.** Audio interviews will be transcribed and then coded in nVivo software. Transcription and analysis will be iterative; initial findings may influence the interview guide and future questions asked. Using NVivo, a directed content analysis will identify key themes in structured interviews. Interviews will be discussed by the research team including qualitative research mentors to achieve consensus in the coding framework. All interviews will be double coded by myself and a trained research assistant. Analysis will be guided by the Applied Thematic Approach to identify barriers and facilitators for XR-B initiation at individual, and organizational levels. Themes will be coded and compiled in a codebook which will include iPARIHS domains *a priori* and other codes that emerge from the data.

**Costs to Subjects.** There are no costs to subjects for participations. This research will not affect standard treatment or routine care in any way. There are no risks above minimal risk as detailed below.

**Subject Compensation.** Upon completion of the interview, all participants will receive \$25 reimbursement for their time via electronic gift-card or commissary deposit, as has been done in previous studies approved by the IRB and the RIDOC. The compensation will be consistent with previous amounts (i.e. \$25) that have not been found to be associated with coercion but that adequately compensate individuals for their time. If staff are unable or unwilling to receive \$25, we will offer to donate the \$25 to a charity of their choice and provide them with receipt.

**BENEFITS:**

Data received from this study could positively impact future medical services to participants in a way that is equal to others that suffer from similar medical problems.

For organizational stakeholders, it may provide a more streamlined approach to deliver medications and reduce diversion or other security risks.

**RISKS TO SUBJECTS:**

The risks are minimal and those associated with other qualitative studies, namely: emotional distress and breach of confidentiality. Both of these risks will be minimized in as many ways as possible to ensure the participants are emotionally supported, can stop the interview at any time, and feel no pressure to give specific answers or talk about topics they'd prefer to omit. Confidentiality will be maintained through encryption, password-protection, and limited only-when-needed use of any identifiable data and by as few research staff as possible to maintain research operations.

**INFORMED CONSENT if applicable:**

Informed consent will be obtained at the time of the interview. All participants will be asked to sign an informed consent document and will be offered a copy of this form. The Informed Consent form will be written at a level the subjects will understand, at an elementary-school reading level as per RIDOC guidelines. The person obtaining consent will provide the participant the opportunity to ask any questions related to the study before the participant signs any consent form.

**CONFIDENTIALITY OF DATA:**

All participant data will be kept confidential. Survey data will be anonymous. Qualitative interview data will be kept confidential. Audio files and transcripts will be identified by participant ID only. The participant's identification number will only be connected to the participant's name through a single encrypted password-protected master file kept on password-protected computers, accessible only to approved research staff. We will protect all other data files with passwords and lock any paperwork in cabinets.

All digital recordings will be uploaded to the HIPAA-compliant nVivo AI transcription service within 24 hours of recording. Transcripts will be cleaned by a member of the research team and all PHI will be redacted from the transcriptions within 1 week of transcription. The PI will then certify each transcript as complete, at which time the original audio files will be deleted within 2 weeks.

The study will also be approved by the Medical Research Advisory Group (MRAG) at the Rhode Island Department of Corrections (RIDOC). All research will be conducted in a manner consistent with the highest ethical standards using these multiple oversight groups as well as collaboration with the COBRE for Opioids and Overdose Community Advisory Board and in line with previous NIH-supported research conducted at the RIDOC.

No data will be published that could allow for a reader to track responses back to an individual.

Survey data will be entered into REDCap. Thus, the Lifespan Hospital System will be used as the central location for data management. Vanderbilt University, with collaboration from a consortium of institutional partners, developed a software package for electronic collection and management of research and clinical trial data known as REDCap (Research Electronic Data Capture). The REDCap system provides secure, web-based applications that can be used for various types of research and operational support purposes, as well as provide an intuitive interface for users to enter data with real-time validation rules (with automated data type and range checks) at the time of entry. These systems offer easy data manipulation with audit trails for reporting, monitoring, and querying patient records, and an automated export mechanism to common statistical packages (SPSS, SAS, Stata, R/S-Plus). REDCap servers are housed in a local data center at Lifespan, and all web-based information transmission is encrypted. REDCap was developed specifically around HIPAA-Security guidelines. REDCap has been disseminated for use locally at other institutions and currently supports 240+ academic/non-profit consortium partners on six continents and over 26,000 research end-users ([www.project-redcap.org](http://www.project-redcap.org)). During the study, real-time data transmissions from the study site computers to the centrally housed server will be encrypted using SSL and public key encryption technology. All information will only reference a participant identification number. The participant's identification number will only be connected to the participant's name through a single master file kept on password-protected computers, accessible only to research staff at each study site. We will protect all other data files with passwords and lock any paperwork in cabinets in the PI's office.

The interview will contain sensitive questions about community drug use and medication diversion while incarcerated. As this is an NIH-funded study, there will be an automatic Certificate of Confidentiality applied. Per the NIH website, "**Information protected by a CoC is immune from the legal process and is not admissible as evidence (unless participant consents to this disclosure).**" This information will be shared with the participant. Topics of mandatory reporting (i.e., elder abuse, child abuse, suicidality, sexual contact as protected by the Prison Rape Elimination Act (PREA)) will be discussed and the participant will be informed that this information, if discovered, will be reported to the Warden of the facility. The research staff member will follow all mandatory reporting policies. A statement will be made that confidentiality must be broken if information revealed is considered a threat to self, facility, and/or community corrections security. A statement will be made that parole boards will not consider a prisoner's participation in the research in making decisions regarding parole. The mailing address for the PI and Lifespan HRPP will be included.

All persons who will be conducting evaluative research are informed of, and agree in writing to conform to, all applicable RIDOC policies including, but not limited to, those pertaining to the confidentiality of information obtained per the RIDOC Confidentiality Pledge.

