#### **DATA SAFETY AND MONITORING PLAN:**

Though all participants will face no more than minimal risk, the inclusion of a vulnerable population (prisoners) and setting warrant additional assurances regarding a data safety and monitoring plan. In addition to the privacy considerations of participants, confidentiality considerations of participant data, and assurances of appropriate informed consent as above, additional safety and monitoring will include:

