##### Monitoring the safety of the participants

The recruitment and interview of incarcerated can occur during routine clinical times, namely during group sessions or meeting with clinicians. Therefore, if any safety risk arises, the clinical

staff will be alerted immediately. Moreover, this recruitment setting provided additional privacy considerations within a healthcare setting. The research assistant (RA) will be trained specifically to work with this study population. While organizational stakeholders face less vulnerability to data, similar protections will be offered to protect their privacy and consideration during the recruitment and interview process.

All research staff members will receive training related to DOC policies on the Prison Rape Elimination Act and mandatory reporting. Study staff will receive training on maintaining a calm, empathetic demeanor while speaking to study participants. Study staff will immediately notify the PI for any information that may require mandatory reporting and the PI will provide a report to an appropriate contact at the Department of Corrections (i.e., Special Investigations Unit) if the material disclosed does require reporting. Instances requiring mandatory reporting (i.e., PREA allegations, threats to staff or other individual) will be explicitly disclosed during the informed consent process. The PI will be available to the RA by phone and email at all times. All instances of possible will be discussed in weekly supervision and/or team meetings with PI and study staff.

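### Participants are told that mandatory reports go to the Warden, but the PI's reporting route names the Special Investigations Unit, and the protocol does not connect the two

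*Protocol*

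**What the plan says.** Two sections of the Protocol deal with mandatory reporting.

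- **Confidentiality of data.** The items are given as "Topics of mandatory reporting (i.e., elder abuse, child abuse, suicidality, sexual contact as protected by the Prison Rape Elimination Act (PREA", and participants are to be told that "this information, if discovered, will be reported to the Warden of the facility". A separate statement to participants says that "confidentiality must be broken if information revealed is considered a threat to self, facility, and/or community corrections security"; it names no recipient. The section also says: "The research staff member will follow all mandatory reporting policies".
- **Monitoring the safety of the participants** (in the data safety and monitoring plan). Staff alert the PI to anything that might have to be reported, and the PI then reports to "an appropriate contact at the Department of Corrections (i.e., Special Investigations Unit) if the material disclosed does require reporting". On what participants hear: "Instances requiring mandatory reporting (i.e., PREA allegations, threats to staff or other individual) will be explicitly disclosed during the informed consent process".

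The introduction to the monitoring plan presents its measures as coming "In addition to the privacy considerations of participants, confidentiality considerations of participant data, and assurances of appropriate informed consent as above". It gives the inclusion of prisoners as the reason for these extra assurances.

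**The concern.** One section fixes what a participant is told about the destination of a report. The other fixes where the PI sends it. The named offices differ, and neither section refers to the other.

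The participants most affected are incarcerated, and what they disclose may have consequences in custody. A person deciding what to say in an interview may reasonably weigh who will learn of it. If the stated recipient is wrong or incomplete, consent rests on an inaccurate description of the procedure, in a population for which the Protocol itself says more care is due. What is at stake is the accuracy of consent and the destination of disclosures. The sample size, the coding and the themes are not in question.

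**Working it through.** No arithmetic bears on the conclusion, and the plan gives no figure to reproduce. The check sets the two sections side by side.

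| | Confidentiality of data | Monitoring the safety of the participants |
|---|---|---|
| Named items | elder abuse; child abuse; suicidality; PREA-protected sexual contact (4) | PREA allegations; threats to staff or another individual (2) |
| Further statement | threat to self, facility or community corrections security (1) | none |
| Recipient | Warden for the 4 named items; none named for the security statement | Special Investigations Unit |
| What the recipient sentence describes | what the participant is told | what the PI does |

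**Step 1: which items the recipient mismatch covers.** The sentence naming the Unit is conditional only on the material requiring reporting. It is not limited to PREA allegations or to the two items listed later in the same section. It therefore reaches all 4 topics for which participants are told the Warden.

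**Step 2: possible readings of the recipient.**

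- Only the Warden receives reports: the statement to participants is right and the PI's route is wrong.
- Only the Unit receives reports: the PI's route is right and participants are told the wrong office.
- Both receive reports: neither sentence is false, but participants hear of one recipient out of two.
- The appropriate contact is chosen case by case and the Unit is only an example: the sections agree when the Warden is chosen and disagree when the Unit is. This reading needs the Protocol's *i.e.* to mean *for example*.

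Only the last reading can remove the mismatch, and then only for some reports. No sentence in the Protocol selects among the four. The section on adverse events sends participants with significant mental health concerns to the corrections healthcare service, but that is a referral for care and does not settle who receives a mandatory report.

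**Step 3: the lists.** PREA is the one item named in both. Of the 4 topics in the confidentiality section, 4 − 1 = 3 are not repeated in the monitoring plan. Of the 2 items in the monitoring plan, 1 is named in the confidentiality section, and both are covered if threats to staff or another individual fall under the security statement. Taken together, the sections give 4 + 1 = 5 categories if those threats are read into the security statement, and 5 + 1 = 6 if they are not. Since the monitoring plan adds to the consent assurances before it, the lists combine. What remains is a difference of wording between two lists that each read as complete.

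**The case against.** The strongest reply is that the two sentences do different jobs and are compatible. One tells the participant about the Warden and the other describes the PI's route. Neither says that its recipient is the only one, and a Department of Corrections contact could include the Warden. This stands in part: the sections do not strictly exclude each other, and a report to both offices would satisfy both. It does not remove the point. The Protocol does not say that both receive the report, its wording narrows the contact to the Unit, and under a dual route participants would still be told of only one recipient.

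A second reply is that the consent form and interview guides are listed as attachments, are not shown here, and may already be clear. That is possible. Clear consent wording would correct what participants are told, but the two Protocol sections would still disagree.

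Three stronger readings are tempting, and the documents do not support them.

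- *A reader might infer that consent will leave out elder abuse, child abuse and suicidality.* That follows only if the form were drafted from the monitoring plan alone. Nothing says it would be, and the plan's introduction makes it additional to the earlier assurances.
- *A reader might infer that staff act on a narrower scope than participants are told.* Staff are to bring the PI anything that might need reporting, are trained in the corrections policies, and are bound by the sentence "The research staff member will follow all mandatory reporting policies". The short list does not limit their conduct.
- *A reader might infer a conflict between the planned questions on medication diversion and the security exception.* The Protocol says that "The interview will contain sensitive questions about community drug use and medication diversion while incarcerated" and also states the exception. Whether a diversion account triggers it depends on corrections policy that is not shown. That is unstated detail, not a contradiction.

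**Conclusion.** The recipient disclosed to participants does not match the route that the PI is to follow, and the Protocol leaves the two unconnected. The mismatch extends to all 4 topics named to participants, not to PREA alone. The difference between the two lists is a wording mismatch and not a shown omission.

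This is a minor point: wrong as written and worth correcting because it concerns what prisoners are told. No effect on the study's results is claimed, and none can be estimated from the Protocol. The conclusion assumes that *i.e.* carries its ordinary meaning and that no unseen attachment redefines the reporting route. Which recipient is right is not a question that this review can answer.

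**What to change.** The sponsor, with the IRB and MRAG, should reconcile the confidentiality section and the monitoring plan so that both give:

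1. one reporting route, which may name more than one recipient and should also cover the security statement; and
2. one combined list of reportable items.

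The same wording should go into the consent form, so that participants are told every recipient on the agreed route. The choice of recipient belongs to those bodies.

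The cost is wording in two Protocol sections and the consent form. Consent is taken at the interview, and MRAG review of privacy and confidentiality is already planned, so no further contact with participants, data or recruitment is needed.

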#### **DATA SAFETY AND MONITORING PLAN:**

Though all participants will face no more than minimal risk, the inclusion of a vulnerable population (prisoners) and setting warrant additional assurances regarding a data safety and monitoring plan. In addition to the privacy considerations of participants, confidentiality considerations of participant data, and assurances of appropriate informed consent as above, additional safety and monitoring will include:

